16.2 Definition of analysis sets

All main descriptions and analyses of safety and efficacy data will be based on the FAS, as defined in ICH E9 Guidelines (Statistical Principles for Clinical Trials). The FAS includes all dosed patients with data after dosing.

The ABR will also be summarised by the following subgroups:

Cause of bleed (Spontaneous, Traumatic, Re-bleed), Site of bleeding (Central nervous system, Haemarthrosis (Joint), Gastrointestinal, Subcutaneous, Muscular or other), Classification of bleeding (Mild/Moderate or Severe)

16.2.1 Handling of exceptional pharmacokinetic outlier data

Exceptional outlier PK profiles and/or individual plasma concentrations may be excluded when analysing PK endpoints based on the FAS. If exceptional outlier data are identified, a sensitivity analysis including the outlier data will be conducted.

Unless otherwise stated, analysis results obtained from FAS excluding exceptional outliers will be presented with reference to the “full analysis set excluding outliers”. The results of the sensitivity analysis including the exceptional outliers will refer to “full analysis set incl. all data”.

16.2.2 Documentation of analysis sets

The decision to exclude data points from analysis of PK endpoints based on the FAS will be made from a review prior to database lock. It will be the joint responsibility of the clinical pharmacology scientist and the trial statistician.

The profiles or observations to be excluded from the FAS and the reason for their exclusion will be documented and signed by the clinical pharmacology scientist and the trial statistician as part of the database lock minutes. The documentation will be stored together with the remaining trial documentation. This will also be described in the CTR.

16.3 Primary endpoint

- Haemostatic effect of turoctocog alfa when used for treatment of bleeds, assessed on a four-point scale for haemostatic response (excellent, good, moderate and none) during the main phase (6 months duration per patient).

In addition treatment success will be summarised by counting haemostatic responses rated as good or excellent as success and responses rated as moderate and none as failure. If the haemostatic response is missing, the response will be counted as failure in the primary analysis, but a sensitivity analysis will be performed excluding bleeding episodes with missing response. Treatment success will also be summarised excluding data from low titer periods as a sensitivity analysis to the primary analysis.

The haemostatic effect of turoctocog alfa will also be summarised by the following subgroups: Cause of bleed (Spontaneous, Traumatic, Re-bleed), Site of bleeding (Central nervous system, Haemarthrosis (Joint), Gastrointestinal, Subcutaneous, Muscular or other), Classification of bleeding (Mild/Moderate or Severe)

Analyses and presentations will be made by age groups, type of regimen, trial phase and total.

16.4 Supportive secondary endpoints

All the following endpoints will be analysed for the main and extension phase and the combined main and extension phase data.

16.4.1 Efficacy endpoints

The primary endpoint will be repeated for the extension phase and the combined main and extension phase (total trial period of 24 months). The analysis is similar to the primary analysis

Number of bleeds (total bleeds assessed as annual bleeding rate) per patient during both the main phase of 6 months and the trial period of 24 months. This endpoint will only be presented for patients on prophylaxis regimen and will be reported using only treatment requiring bleeds.-The following sensitivity analyses will be performed:

- The annualised bleeding rate will be calculated for both treatment-requiring bleeds and non-treatment requiring bleeds
- The annualised bleeding rate will be calculated excluding data from low titer periods

The annualised bleeding rate will be analysed by a negative binomial model and estimated annualised bleeding rate with confidence interval will be presented by trial phase and treatment regimen. As a sensitivity analysis, a Poisson model with over-dispersion will also be applied. Analyses and presentations will be made for the preventative regimen by age groups, trial phase and total.

When turoctocog alfa is administered via a butterfly, the dead space is subtracted from the total volume of the dose to account for the compound left in the butterfly device after injection.

- Consumption of turoctocog alfa for bleeding treatment (average dose to treat a bleed, number of injections and IU/kg per bleed) during both the main phase of 6 months and the trial period of 24 months

This endpoint will be summarised and listed. The presentations will be made by age groups, type of regimen, trial phase and total.

- Consumption of turoctocog alfa during prophylaxis treatment (average prophylaxis dose, number of injections and IU/kg per month and per year) per patient during both the main of 6 months and the trial period of 24 months

This endpoint will be summarised and listed. The presentation will be made for the preventative regimen by trial phase, age groups and total.

- Total consumption of turoctocog alfa (IU/kg per month and per year) per patient during both the main phase of 6 months and the trial period of 24 months. This endpoint will be summarised and listed. The presentation will be made by type of regimen, trial phase, age groups and total
- Surgery-related endpoints where applicable:

- Haemostatic effect evaluated on the four-point scale (excellent, good, moderate and none) and assessed by the investigator/surgeon at the day of surgery (Day 1) and on the last day in the post-operative period the patient is at the trial/surgery site
- Loss of blood and requirements for transfusion on the day of surgery (Day 1) and during the post-operative period Days 2-7 or until the last day the patient is at the trial/surgery site whatever comes first

Surgery-related endpoints will be summarised by trial phase and listed.

16.4.2 Safety endpoints

- Incidence rate of inhibitory antibodies against factor VIII (≥ 0.6 BU) during both the main phase of 6 months and the trial period of 24 months

The incidence rate of inhibitors (≥ 0.6 BU) represented as the percentage of patients developing inhibitors will be calculated and a 1-sided 97.5% upper confidence limit will be provided based on an exact calculation for a binomial distribution. For the calculation of the incidence rate the numerator will include all patients with inhibitors while the denominator will include all patients in the trial exposed to turoctocog alfa.

FVIII activity (trough) at baseline will be compared graphically between patients with and without inhibitors. HLA genotype will be cross tabulated against the presence of inhibitors

- Frequency of Adverse Events (AEs) and serious adverse events (SAEs) reported during both the main phase of 6 months and the trial period of 24 months. AEs and SAEs reported during the study will be summarised by frequency of events and frequency of patients with any event. Similar summaries cross-classified by severity will also be made. The summary tables will be made by patient with and without inhibitors (< 0.6 BU), trial phase, age groups, type of regimen and total.

Furthermore, listings will be provided displaying all AEs and SAEs reported during the study including pertinent clinical information. For patients exposed to both vial strengths the strongest causality will be used in summary tables. In listings both causalities will be displayed for relevant events in these patients.

- Adverse Events/Serious Adverse Events occurred on the day of surgery (Day 1) and during the post-operative period Days 2-7 or until the last day the patient is at the trial/surgery site whatever comes first

AEs and SAEs at the day of surgery (Day 1) and during the post-operative period Days 2-7 will be summarised by frequency of events and frequency of patients with any event. Similar summaries cross-classified by severity will also be made.

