5.1 Type of trial

This is a single-country, multi-centre, open-label and non-randomised trial. 65 PTPs with haemophilia A will be given a prophylactic regimen or an on-demand regimen of turoctocog alfa. It is not possible to switch between these 2 treatments regimens in the main phase of the trial, but the dose and frequency of dosing can though be changed. (Please see 5.3.1 for exemption of patients with low titer inhibitor) At least 10 patients on the on-demand and 20 patients on the prophylaxis regimen will complete the main phase of the trial, which will last for approximately 6 months.

If a patient has not finalised the main phase at the time of cut off for the main CTR they will though be moved to the extension phase of the trial and thus will not complete the main phase and will not have 6 months in this phase of the trial. See [Figure 16–1](#). They will though have the visit 8 safety assessments performed at the last main visit or at the next extension visit.

For an individual patient the main phase is defined as from visit 1 to visit 8. On trial level the main CTR will be written with at least 60 patients having completed the main phase of the trial.

An extension phase (from visit 8 until LPLV, see section [7](#)) is added to assess long term safety and efficacy, see section [7](#), and either prophylaxis or on demand treatment can be chosen also in this phase, but it is possible to switch between these treatments regimens during the extension phase and also to change the dose and frequency of dosing.

Of the 65 dosed patients, a minimum of 12 and a maximum of 18 patients (see [Table 6–1](#)) will be enrolled in the PK session to characterise the PK profile of turoctocog alfa in a Chinese population with severe haemophilia A.

Enrolled patients who need to undergo surgical procedures will remain in the trial provided that turoctocog alfa is used for the prevention and treatment of the surgical bleeding. All surgeries procedures (e.g. minor, major, elective, and emergency) may be performed using turoctocog alfa at the investigators discretion.

[figure not shown]

Figure 5–1 Overview of the trial design

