Patients that are withdrawn from the trial due to inhibitor development will be followed up at 3 follow-up visits scheduled with a month apart.

7 Milestones

Planned duration of recruitment period: First patient first visit until last patient first visit in the main trial (FPFV – LPFV in the main trial): 12 months

Planned FPFV: 15-Dec-2016

End of trial is defined as last patient last visit (LPLV):

- Planned LPLV for the main phase of the trial: 15-Jun-2018
- Planned LPLV for the extension phase of the trial: 15-Dec-2018

The total duration for a patient's participation in the trial is expected to be 6 months in the main phase of the trial and at most 18 months in the extension phase of the trial or until turoctocog alfa is commercially available or until the marketing authorisation application is rejected in China or until the trial, part of the trial or a trial site is terminated by Novo Nordisk or by a relevant authority for any reason. In any event, the LPLV for the trial will be no later than 18 months from FPLV in the main trial, which is planned to be the 15-Dec-2018 whether or not the product is commercially available in China.

If a patient has not finalised the main phase at the time of the cut off for the main CTR they will be moved to the extension phase of the trial and thus will not have 6 months in the main phase of the trial. See [Figure 16-1](#)

Recruitment:

The different age groups in the PK and main phase of the trial will be open for recruitment from the beginning of the trial. The extension phase will first open for a patient when he has finalised the main phase.

Trial registration:

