- Next visit should be scheduled

8.1.2 Visit 2

The visit must be scheduled 14 days after the screening visit with a window of 4 days. This is to allow sufficient time for the arrival of the laboratory reports as all results necessary for evaluation of the inclusion and exclusion criteria must be available before determining whether or not the patient can continue in the trial.

The main purpose of visit 2 is to inject the trial product the first time after the final evaluation of the inclusion and exclusion criteria and to assess the patient's medical status after the first dose of turoctocog alfa. This is also applicable for patients on the on-demand regimen and will need to record this dose as another dose. The investigator must also hand out the diary and train how to use it. Furthermore the visit can also be attended for PK assessments, see section [8.1.2.1](#).

It is not possible to change between the prophylactic and on-demand regimen during the main phase. (Please see [5.3.1](#) for exemption of patients with low titer inhibitor) It is possible to switch between the 2 different prophylactic dosing frequencies at a visit to the trial site in the main phase. However, if the patient changes regimen from three times weekly to every second day the site should contact the monitor at least seven days before the next scheduled visit so as to ensure there is sufficient trial product at site.

The investigator must judge if the patient or parent/caregiver capability of handling the trial product injection and plan for home training at unscheduled visits if necessary.

Trial product for home treatment must be dispensed to the patient or parent/caregiver if necessary until next visit.

In case the patient will have a PK session the first dose at visit 2 is administered for PK, see section [8.1.2.1](#).

The assessments to be performed at this visit are listed in section [2](#).

Key reminders:

- Ask if the patient has experienced any AEs since last visit
- Ask for any concomitant medications since last visit
- Training for home injection
- Dispensing session for the first dose and dispensing trial product until next visit must be performed in the IWRS
 - In case the patient will perform PK the first dose must be a PK session, see section [8.1.2.1](#)
- Drug accountability must be performed in the IWRS for the first dose
- Hand out diary
- Check for 48 hours washout of FVIII products before inhibitor test
- Trial product must be dispensed

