8.1.4 Visit 9 and visit 10 (Dispensing visits) – extension phase

The dispensing visits in the extension phase must be scheduled 56 days (approximately 2 months) after the previous visit with a window of 2 weeks. The main reason for these visits is to dispense trial product to the patient or parent/caregiver. In case the patient has a positive inhibitor (≥ 0.6 BU) some laboratory test must also be performed, see section [2](#).

Visit 9 and 10 will be repeated every six months until LPLV with a consecutive visit number see section [7](#).

The assessments to be performed at these visits are listed in section [2](#).

Key reminders:

- Ask if the patient has experienced any AEs since last visit
- Ask for any concomitant medications since last visit
- Dispensing session for trial product until next visit must be performed in the IWRS
- Drug accountability of trial product must be recorded in the IWRS
- Review of the diary
 - Evaluate together with the patient the correctness of the haemostatic efficacy for treatment of bleeds

- Trial product must be dispensed
- Next visit should be scheduled

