Data from central laboratories will be transferred electronically from the laboratory performing the analyses. In cases where data is transferred via non-secure electronic networks, data will be encrypted during transfer.

Both the central and local laboratory will provide all laboratory reports to the investigator for storage at the trial site.

The patient and any biological material obtained from the patient will be identified by patient number and trial identification number. Appropriate measures such as encryption or leaving out certain identifiers will be enforced to protect the identity of patients in all presentations and publications as required by local, regional and national requirements.

15 Computerised systems

Novo Nordisk will capture and process clinical data using computerised systems that are described in Novo Nordisk Standard Operating Procedures and IT architecture documentation. The use and control of these systems are documented.

Investigators working on the trial may use their own electronic systems to capture source data.

16 Statistical considerations

Evaluation of data will be based mainly upon descriptive statistics, i.e. summary tables, listings, and figures. Categorical data will be summarised by frequency tables while continuous data will be summarised by mean, standard deviation, minimum and maximum value.

All efficacy endpoints will be reported only for patients without inhibitors (<0.6 BU) and using bleeds with turoctocog alfa treatment. Base on the full analysis set (FAS), but if a patient develops an inhibitor only the time before the positive inhibitor test will be used to evaluate the efficacy endpoints. The following sensitivity analyses will be performed:

- The annualised bleeding rate will be calculated for both treatment-requiring bleeds and non-treatment requiring bleeds
- The annualised bleeding rate will be calculated excluding data from low titer periods
- Treatment success will be summarised excluding data from low titer periods

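### AE and SAE tables split by trial phase and regimen carry no person-time, so their figures mix event rate with length of follow-up

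*Protocol*

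**What the plan says.** Protocol 16.4.2 gives two measures for AEs and SAEs: "AEs and SAEs reported during the study will be summarised by frequency of events and frequency of patients with any event". The tables are broken down by inhibitor status and by "trial phase, age groups, type of regimen and total". The SAP section on safety endpoints uses the same words, and SAP section 3 reports no changes from the protocol. The general rule in Protocol section 16 is "Categorical data will be summarised by frequency tables while continuous data will be summarised by mean, standard deviation, minimum and maximum value". Neither document mentions patient-years or an event rate for AEs.

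The same plan does standardise other endpoints for time. In 16.4.1, bleeds become an annualised rate presented by phase and regimen, and consumption is given per month and per year.

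On phase length, section 7 expects "6 months in the main phase of the trial and at most 18 months in the extension phase of the trial", and 5.1 adds: "For an individual patient the main phase is defined as from visit 1 to visit 8". Patients still in the main phase at the main CTR cut-off are reported there with the data they have, and the extension data available by then go into the same report (section 16). Regimen is fixed in the main phase, apart from a low-titre inhibitor exception, but may be switched in the extension (5.1, 5.3.1).

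**The concern.** A count of events, or of patients with any event, grows with time observed. When columns cover different lengths of time, the same underlying rate gives different figures, and a real change in rate can be hidden or exaggerated.

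This matters here for two reasons. AE and SAE frequency is a secondary endpoint selected for public posting (4.2.2). The extension was also added to look at long-term safety (5.1), and readers will naturally look to the phase columns for that.

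The regimen columns have a related problem in the extension and in the combined data. A patient who switches contributes time to both regimens, and the documents do not say how that patient's events are assigned.

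**Working it through.** The documents give no AE rate, so the event rates below are assumptions chosen to show scale.

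**Length of the main phase**
- Visit 1 to 2 is 14 days (8.1.2: "The visit must be scheduled 14 days after the screening visit with a window of 4 days"). Visit 2 to 3 is 14 days, and visits 3 to 8 are five intervals of 28 days (8.1.3).
- Visit 1 to 8: 14 + 14 + 5 × 28 = 168 days.
- First dose (visit 2) to visit 8: 14 + 5 × 28 = 154 days.

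**Length of the extension, on the dates in section 7**
- The plan's 24-month total reproduces as 6 + 18.
- Longest: 18 months = 18 × 30.44 = 548 days, for the first patients entered.
- Shortest: 15 June to 15 December 2018 = 183 days, for the last patients entered.

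**Ratio of extension to main phase**
- Longest extension: 548/168 = 3.3 from visit 1, 548/154 = 3.6 from first dose, 18/6 = 3.0 in nominal months.
- Shortest extension: 183/168 = 1.1 from visit 1, 183/154 = 1.2 from first dose, 6/6 = 1.0 in nominal months.

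**Effect on the tabulated figures**

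With constant rate r per year and time t in years, expected events per patient are r × t, and the share with at least one event is 1 − exp(−r × t).

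| Assumed r | Main phase, 154 to 168 days | Extension, 6 months | Extension, 18 months |
|---|---|---|---|
| 0.5 | 19% to 21% | 22% | 53% |
| 1 | 34% to 37% | 39% | 78% |
| 2 | 57% to 60% | 63% | 95% |

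At r = 1, events per patient are 0.42 to 0.46 in the main phase and 0.50 to 1.50 in the extension.

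**Dependence on the report**

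Take r = 1, even recruitment and no dropout.
- Updated CTR: extension time is spread over 0.5 to 1.5 years. The average share is 1 − (exp(−0.5) − exp(−1.5)) = 1 − (0.607 − 0.223) = 62%.
- Main CTR: assume the cut-off falls near the planned last main-phase visit of 15 June 2018. Extension time is then spread over 0 to 1 year, and the average share is 1 − (1 − exp(−1)) = 37%.

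One true rate thus gives an extension figure close to the main-phase figure in one report and well above it in the other.

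**With person-time**

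At r = 1, the main phase gives 0.42/(154/365.25) = 1.0 per patient-year, and an 18-month extension gives 1.50/1.50 = 1.0. The difference due to duration disappears.

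**Intensity of observation**
- Scheduled visits go from 28 to 56 days apart; under 8.1.4 the dispensing visits "must be scheduled 56 days (approximately 2 months) after the previous visit with a window of 2 weeks".
- Routine haematology and biochemistry are at visits 1, 5 and 8, each 84 days apart (365.25/84 = 4.3 per year). In the extension they are at assessment visits, 3 × 56 = 168 days apart (2.2 per year).

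**The case against.** The trial is uncontrolled and mainly descriptive, and no test of main phase against extension is planned. The AE endpoint is worded as a 6-month figure and a 24-month total, so unequal duration is plain from the endpoint itself. The primary conclusion uses main-phase data only. All of this stands: no estimate, test or error rate is at risk, only the reading of columns set side by side.

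A reader might infer more than the documents support:
- **That the plan rules out rates, or commits to percentages.** It does neither. It speaks of frequency of events and of patients, and leaves a rate unspecified.
- **That the phases differ 3.6-fold.** That is the maximum, counted from first dose. On the protocol's own definition it is 3.3, and for late entrants about 1.1. It also does not describe the main CTR, where extension follow-up is partial.
- **That the extension must show more patients with AEs.** Section 6.1 plans 65 starters and 50 extension completers. At 1 event per year and 6 months of extension, 39% of 50 is about 20 patients, against 34% of 65, about 22, in the main phase.
- **That wider visit spacing means AEs go uncounted.** Enquiry covers the whole time since the last visit. AEs are also asked about at every contact and every unscheduled visit, and diaries are reviewed for them. Spacing may affect recall and the detection of laboratory abnormalities, but the documents allow no estimate of any loss. This is a minor point.

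**Conclusion.** The point holds as a cheap improvement to presentation. As specified, AE and SAE figures by phase and regimen combine event rate with follow-up time. The time ratio between phases runs from about 1.1 for late entrants to a maximum of 3.0 to 3.6, depending on where the main phase is taken to start. Follow-up also varies within each phase.

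At an assumed constant 1 event per patient-year, the duration difference alone separates 34% to 37% in the main phase from 39% to 78% over 6 to 18 months of extension. The percentages rest on that assumed rate and on the planned dates. The need for a time denominator does not: it follows from unequal follow-up alone. The direction of the distortion cannot be fixed in advance, because it depends on which report is read and on dropout.

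**What to change.** In Protocol 16.4.2 and the SAP safety section, add patient-years of exposure and events per patient-year to the AE and SAE summary tables, by trial phase and regimen. Assign events and time to the regimen in use when they occur. Use one start date for both events and time. State that any reading across phases or regimens rests on these rates. Keep the planned counts.

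Optionally, add a footnote that in the extension scheduled visits go from every 28 to every 56 days, and routine haematology and biochemistry from every 84 to every 168 days. A rate removes the effect of duration but not any difference in detection.

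The cost is a sentence or two of text and one or two columns, from visit and injection dates already recorded. The downside is slightly larger tables. Trial conduct does not change.

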4.2.2.2 Surgery endpoints

The surgery endpoints will be evaluated both for the main phase of the trial (6 months duration per patient), and for the combined main and extension phase (total trial period of 24 months).

- Haemostatic effect evaluated on the four-point scale (excellent, good, moderate and none) and assessed by the investigator/surgeon on the day of surgery (Day 1) and on the last day in the post-operative period the patient is at the trial/surgery site
- Loss of blood and requirements for transfusion on the day of surgery (Day 1) and during the post-operative period Days 2-7 or until the last day the patient is at the trial/surgery site whatever comes first
- Adverse Events/Serious Adverse Events occurred on the day of surgery (Day 1) and during the post-operative period Days 2-7 or until the last day the patient is at the trial/surgery site whatever comes first

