8.1.6 Surgery visits - main and extension phase

Patients undergoing surgery will continue the regular visit schedule and will not need to reschedule visits during the surgery period, except if the surgery treatments do not allow for the necessary washout period of 48 hours, then the visit must be re-scheduled.

The surgery and the injection of trial product during the surgery and in the post-operative period will be recorded in the eCRF, except if the injection is performed at home or at another site as these doses will be recorded in the diary and then later transferred into the eCRF by the trial site. For more information regarding surgery see section [8.3.5](#). The post-operative period is defined as the period the patient is not following his ordinary planned treatment regimen after the surgery has been performed.

The assessments to be performed at this visit are listed in section [2](#).

Key reminders:

- Ask if the patient has experienced any AEs since last visit
- Ask for any concomitant medications since last visit
- Dispensing session for trial product during surgery must be performed in the IWRS
- Before the surgery day the patient must have a negative inhibitor test and a satisfactory recovery test from central laboratory, except for emergency surgery, see section [8.3.5](#)
- Evaluate if a PK is necessary especially before a major surgery.

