11.2 Reporting of adverse events

All events meeting the definition of an AE must be collected and reported. This includes events from the first trial-related activity after the patient has signed the informed consent until the end of the post-treatment follow-up period (last follow-up visit). The events must be recorded in the applicable eCRF or CRF (case report forms) in a timely manner, see timelines below and [Figure 11–1](#).

During each contact with the trial site staff, the patient must be asked about AEs and technical complaints, for example by asking: "Have you experienced any problems since the last contact?"

The patient or parent/LAR should though only be asked about technical complaints if they inject the trial product at home.

All AEs, observed either by the investigator or by the patient, must be reported by the investigator and evaluated. Novo Nordisk assessment of expectedness is performed according to the following reference document: Current version of Investigator's Brochure⁵ and any updates thereto.

All AEs must be recorded by the investigator on an AE form. The investigator should report the diagnosis, if available. If no diagnosis is available, the investigator should record each sign and symptom as individual AEs using separate AE forms.

For SAEs, a safety information form must be completed in addition to the AE form. If several symptoms or diagnoses occur as part of the same clinical picture, one safety information form can be used to describe all the SAEs.

MESIs, regardless of seriousness, must be reported using both the AE form (by ticking of the MESI criterion) and the safety information form.

The AE form for a non-serious AE should be signed when the event is resolved or at the end of the trial.

Timelines for initial reporting of AEs:

The investigator must complete the following forms in the CRF/eCRF within the specified timelines:

- **SAEs:** The AE form in the eCRF **within 24 hours** and the paper safety information form (SIF) **within 5 calendar** days of the investigator's first knowledge of the SAE.

The AE form in the eCRF must be signed within 7 calendar days from the date the information was entered in the eCRF.

- **Non-serious AE fulfilling the MESI criteria:** The AE form in the eCRF and the paper SIF **within 14 calendar days** of the investigator's first knowledge of the event
- **Hypersensitivity questionnaire:** **Within 14 calendar days** of the investigator's first knowledge of the event

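### The surgical AE/SAE endpoint is given two conflicting windows, one ending when the patient leaves the site and one running to Day 7, with no stated denominator

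*Protocol*

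**What the plan says.** Protocol 4.2.2.2 lists as a surgery endpoint "Adverse Events/Serious Adverse Events occurred on the day of surgery (Day 1) and during the post-operative period Days 2-7", and ends the window early if the patient leaves the site before Day 7. Protocol 16.4.2 repeats the limit: "during the post-operative period Days 2-7 or until the last day the patient is at the trial/surgery site whatever comes first". The SAP's Safety endpoints section has the same bullet.

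Directly under the bullet, 16.4.2 and the SAP state what will be produced: "AEs and SAEs at the day of surgery (Day 1) and during the post-operative period Days 2-7 will be summarised by frequency of events", followed by the frequency of patients with any event. This sentence has no discharge limit. The only units named are "frequency of events and frequency of patients with any event"; the text does not say whether the base is patients with surgery, surgeries or days of observation.

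Other relevant text:
- Protocol 4.1 makes the safety of turoctocog alfa during surgery a secondary objective.
- Protocol 11.2: "All events meeting the definition of an AE must be collected and reported", from the first trial activity to the last follow-up visit, on or off site.
- Protocol 16.4.2 also promises that "listings will be provided displaying all AEs and SAEs reported during the study including pertinent clinical information".
- Protocol 8.1.6 defines the post-operative period without reference to the site: "The post-operative period is defined as the period the patient is not following his ordinary planned treatment regimen after the surgery has been performed". It expects some of that period to be spent away from the site, since surgery doses go in the eCRF "except if the injection is performed at home or at another site as these doses will be recorded in the diary".
- SAP section 3 reports no changes from the protocol, so it does not settle which window applies.

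**The concern.** Two programmers working from the same plan could produce different surgical AE tables, and each could point to a sentence that supports the result. That alone calls for a correction before database lock.

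The bullet's window also suits a safety endpoint poorly. Presence on site is a natural limit for the haemostatic rating, which is made on the last day there, and for blood loss and transfusion. AEs are collected wherever the patient is. Minor and dental procedures are eligible, so short stays are foreseeable. Under the bullet, a patient who leaves on Day 1 is observed for one day and a patient who stays a week for seven. If patients who recover well tend to leave earlier, observation time is also related to outcome. A table built this way but read as the first post-operative week would understate AE frequency for a stated safety objective.

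**Working it through.** The plan gives no surgical AE rate, length of stay or number of surgeries for this endpoint, so there is no figure to reproduce. The first three steps compare texts; the last two are illustrations on assumed inputs.

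**1. The two windows.** Let d be the last day on site.
- Bullet (4.2.2.2, 16.4.2, SAP): count an AE with onset from Day 1 to Day min(7, d).
- Tabulation sentence (16.4.2, SAP): count an AE with onset from Day 1 to Day 7.

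The windows coincide when d is 7 or more. Below 7, Days d+1 to 7 are in the second and not in the first.

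**2. An example.** Discharge on Day 2, serious AE with onset on Day 4. Bullet: min(7, 2) = 2, and 4 > 2, so it is not counted. Tabulation sentence: 4 ≤ 7, so it is counted. Under either rule it appears in the overall SAE summary and the listing.

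**3. What each window needs.** A fixed window needs the surgery date and the AE onset date. The bullet also needs the last day on site. Table 8-9 lists the surgery data to record and has no such item. It might be inferred from the post-operative haemostatic rating, but for emergency surgery that rating is recorded only where possible.

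**4. Illustration: patients with any event.** Assume a true Day 1-7 probability p7 of 10%, 20% or 30%, a constant daily hazard, and everyone leaving on day d. The probability of an event inside the bullet's window is 1 − (1 − p7)^(d/7).

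| Last day on site | p7 = 10% | p7 = 20% | p7 = 30% | Share of p7 |
|---|---|---|---|---|
| Day 1 | 1.5% | 3.1% | 5.0% | 15-17% |
| Day 3 | 4.4% | 9.1% | 14.2% | 44-47% |
| Day 5 | 7.2% | 14.7% | 22.5% | 72-75% |
| Day 7 | 10% | 20% | 30% | 100% |

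For 10 different patients with one surgery each and p7 = 20%, the chance that none shows an event is (1 − 0.2)^(10d/7): 73% for Day 1, 38% for Day 3, 20% for Day 5 and 11% for the full window.

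**5. Dependence on hazard shape.** The share of events missed is 1 − d/7 under a constant hazard. If the hazard halves every h days, it is 1 − (1 − 2^(−d/h))/(1 − 2^(−7/h)). For d = 5:
- constant: 1 − 5/7 = 29%
- halving every 2 days: 1 − 0.8232/0.9116 = 9.7%
- halving daily: 1 − 0.9688/0.9922 = 2.4%

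The direction is the same throughout, but the size depends on inputs that the documents do not supply.

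**The case against.** The strongest reply is that the tabulation sentence is the only one prescribing an output, and it covers all of Days 2-7. If it is followed, nothing within the week is lost. That is correct, and it limits the point to a conflict with a conditional consequence. It does not remove the conflict, because the sentence can equally be read as shorthand for the bullet above it, in which case the shorter window governs.

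Three stronger readings are tempting, and the documents do not support them:
- *Every surgery stays in the denominator whatever the stay.* No denominator is stated. That is a gap, not a known flaw.
- *Complications after discharge are lost to safety evaluation.* They are collected, summarised in the overall AE and SAE tables, and listed; only the surgical summary could omit them. Disease-related bleeds are mostly not AEs under 11.1, and bleeds from the surgical wound have their own category in Table 8-7.
- *A minimum size of bias can be given, such as 10% for stays up to five days.* It cannot. Step 5 gives 9.7% or 2.4% under plausible declining hazards. If early leavers are also at lower risk, the overall loss is smaller than a common hazard suggests.

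It is also fair that a frequency of on-site AEs is a legitimate, narrower quantity. It misleads only when presented as a Day 1-7 frequency. Finally, the endpoint is descriptive and supportive, with no test attached, and surgeries may be few: Protocol 8.3.5 caps planned major surgeries at 10 in the main phase, although minor and emergency procedures add to that.

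**Conclusion.** The plan states two windows for one endpoint, and the SAP carries both forward. This rests on the text alone and needs no assumption. If the bullet governs, observation time varies with length of stay, AEs with onset after discharge and by Day 7 leave the surgical summary, and the result would understate a Day 1-7 frequency. If the tabulation sentence governs, there is no loss. The amount at stake cannot be derived, since no discharge times or AE rates are given; the tabulated percentages are illustrations under a constant hazard and assumed risks. The primary endpoint and the overall safety reporting are unaffected. The correction is still worth making, because surgical safety is a stated objective and the change is almost free.

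**What to change.** In Protocol 4.2.2.2, Protocol 16.4.2 and the SAP's Safety endpoints section:

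1. Define the surgical AE/SAE window as Day 1 to Day 7 by AE onset date, for every surgery and regardless of discharge. Naming the days alone also avoids dependence on the separate definition of the post-operative period in 8.1.6.
2. Delete the clause that ends the window at the last day on site from the AE/SAE bullet only. Leave the blood loss/transfusion and haemostatic rating bullets as they are, since an on-site limit is natural there.
3. State the denominators: the number of patients with surgery and the number of surgeries. A patient operated on twice then counts once in the first and twice in the second.

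The cost is wording. No visits or data are added, because any day-based window already needs surgery and AE onset dates. The only downside is that the reported surgical AE count may be slightly higher than under the on-site rule.
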